Subjects will be dropped from the arm of the study ingesting daily maintenance dose of peanut protein if they are having moderate to severe clinical symptoms (GI, respiratory or skin) at home after taking the daily dose of peanut protein. Additionally, any subjects who have an accidental peanut ingestion and have anaphylaxis during the time on oral desensitization, will be dropped from the arm of the study ingesting daily maintenance dose of peanut protein. Subjects who experience peanut-related hypotension as evidenced by a 15 % drop in their blood pressure from their baseline, nontransient oxygen desaturation below 90%, recurrent abdominal pain, or recurrent emesis which is felt by the PI to be potentially dose related will be stopped from participating in the study.

Any subject who has a serious adverse event which is felt by the PI to be potentially a result of participation in the study will be dropped from the study.

SAFETY MONITORING

This section defines the types of adverse events that should be reported. It outlines the procedures for the appropriate collection, grading, recording and reporting of the events.

Procedures and Monitoring

All unexpected serious adverse events related to the experimental procedures will be reported to the IRB, DCRU, DSMB, and FDA in a manner consistent with 21 CFR 312.32. All other adverse events related to the experimental procedures will also be reported to the IRB and DCRU in an expedited manner if they are Grade 3 and above in severity. Participant deaths are reportable within 24 hours. The expedited report sent to other organizations will be copied to the DCRU. The investigator will continue to follow or obtain documentation of the resolution course of such an event. A copy of the annual report of adverse events submitted to the IRB will be copied to the DCRU. Reactions to dosing of the study product will be recorded on a dosing log and will not be reported separately as adverse events. Any reaction that meets the criteria for a serious adverse event will be reported both on the dosing log and on an adverse event case report form.

Definitions

Adverse Event (AE) or Medical Event

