An adverse event is a new, undesirable medical event or occurrence or worsening of an existing condition (including an abnormal laboratory finding) in a subject that occurs during treatment and throughout the study, whether or not it is considered to be study related. Adverse events or medical events and toxicities are treatment emergent signs and symptoms.

Potential adverse reactions seen in subjects treated with peanut OIT and subjects undergoing DBPCFC include the following: skin manifestations such as pruritus, urticaria, or angioedema; respiratory symptoms such as wheezing, coughing, nasal congestion/rhinorrhea, cough and hoarseness; and gastrointestinal manifestations such as vomiting, diarrhea, or abdominal pain. Anaphylaxis is a potential risk involving any of the above symptoms plus hypotension and circulatory collapse.

Serious Adverse Event

A serious adverse event is defined as any adverse therapy experience occurring at any dose that results in the following (21 CFR 312.32):

1. Death: A death occurring during the study, or which comes to the attention of the investigator during the protocol-defined follow-up after the completion of therapy whether or not considered treatment related, must be reported.
2. Life-threatening: Any adverse therapy experience that places the subject or subjects, in the view of the investigator, at immediate risk of death from the reaction as it occurred (i.e., it does not include a reaction that, had it occurred in a more serious form, might have caused death).
3. In-patient hospitalizations or prolongation of existing hospitalization.
4. Persistent or significant disability or incapacity.

5. Congenital anomaly/birth defect.
6. An event that required intervention to prevent permanent impairment or damage.

Unexpected Adverse Event

An adverse event is considered “unexpected” when its nature (specificity) or severity is not consistent with applicable product information, such as safety information provided in the protocol or consent.

TOXICITY GRADING

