Toxicity grades are assigned by the study site to indicate the severity of adverse experiences and toxicities using the NCI-CTCAE version 3.0. Toxicity grading for allergic reactions including anaphylaxis is modified from the NCI-CTCAE system to be more appropriate for this study population, and is displayed in Appendix 2. The NCI-CTCAE has been reviewed specifically for this protocol and is otherwise appropriate for this study population. The purpose of using the NCI-CTCAE system is to provide standard language to describe toxicities and to facilitate tabulation and analysis of the data and assessment of the clinical significance of treatment-related toxicities.

Adverse events not included in the CTCAE listing should be recorded and graded 1-5 according to the General Grade Definition provided below:

Grade 1	Mild	Transient or mild discomforts (< 48 hours), no or minimal medical intervention/therapy required, hospitalization not necessary (non-prescription or single-use prescription therapy may be employed to relieve symptoms, e.g., aspirin for simple headache, acetaminophen for post-surgical pain).
Grade 2	Moderate	Mild to moderate limitation in activity some assistance may be needed; no or minimal intervention/therapy required, hospitalization possible.
Grade 3	Severe	Marked limitation in activity, some assistance usually required; medical intervention/therapy required, hospitalization possible.
Grade 4	Life-threatening	Extreme limitation in activity, significant assistance required; significant medical/therapy intervention required, hospitalization or hospice care probable.
Grade 5	Death	Death.

Relationship to Procedure Definitions

Associated: There is a reasonable possibility that the adverse event may have been caused by the test product and/or procedure. This definition applies to those adverse events that are considered definitely, probably or possibly related to the procedure.

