1. **Definitely related:** An adverse event that follows a temporal sequence from administration of the test product and/or procedure; follows a known response pattern to the test article and/or procedure; and, when appropriate to the protocol, is confirmed by finitely related: An adverse event that follows a temporal sequence from administration of the test product and/or procedure; follows a known response pattern to the test article and/or procedure; and, when appropriate to the protocol, is confirmed by improvement after stopping the test product (positive rechallenge: and by reappearance of the reaction after repeat exposure [positive rechallenge]); and cannot be reasonably explained by known characteristics of the subject's clinical state or by other therapies.
2. **Probably related:** An adverse event that follows a reasonable temporal sequence from administration of the test product and/or procedure; follows a known response pattern to the test product and/or procedure, is confirmed by improvement after rechallenge; and cannot be reasonably explained by the known characteristics of the participant's clinical state or other therapies.
3. **Possibly related:** An adverse event that follows a reasonable temporal; sequence from administration of the test product and/or procedure and follows a known response pattern to the test product and/or procedure, but could have been produced by the participant's clinical state or by other therapies.

Not associated: An adverse event for which sufficient information exists to indicate that the etiology is not related to the test product and/or therapy.

1. **Unrelated:** An adverse event that does not follow a reasonable temporal sequence after administration of the test product and/or procedure and most likely is explained by the participant's clinical disease state or by other therapies. In addition, a negative rechallenge to the test article and/or procedure would support an unrelated relationship.

ADVERSE EVENTS COLLECTION PROCEDURES

The Principal Investigator is responsible for collecting and recording all clinical data. As these results are collected, all toxicities and adverse events will be identified and reported to the principal investigator. Adverse events will be reported as described above. The Principal Investigator will determine relationship of the event to the study intervention and decide course of action for the study participant.

Recording and Reporting Procedures

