Cells isolated at entry and every 4 months from individual patients will be incubated for 6 days in triplicate (1 x 10⁶/well in 0.2 ml complete medium) in the presence or absence of *Ara h* 2, CPE (10 μ g/ml) or Con A (2 μ g/ml). Cells will then be pulsed for 18 h with 1 μ Ci [³H] thymidine, harvested, and incorporated radioactivity measured in a β -scintillation counter. Results will be expressed as geometric mean cpm +/- SE with significant proliferation above background (p<0.05) determined by a t test. Protection from anaphylaxis due to Th₂ to Th₁ conversion will result in no significant change in the magnitude of allergen-specific proliferative responses from cells isolated at entry compared to cultures in follow up every 4 months. However, protection mediated by tolerance induction will result in diminished proliferation in peanut-desensitized patients. If diminished proliferation is observed, cultures will be setup in the presence of exogenous IL-2 to distinguish whether decreased proliferation is due either to anergy, which should respond to exogenous IL-2, or due to tolerance, which should not. The presence of CD4+ CD25+ FoxP3+ regulatory T cells will be assessed by flow cytometry. Additionally, we will use ELISPOT kits to quantify the number of IL-10+ peanut-specific T cells over time to determine if this inducible Tr1 type of regulatory T cell develops in treated subjects.

PRELIMINARY RESULTS

Preliminary data from current trials suggest that oral and mucosal immunotherapy for food allergy is safe and effective. 28 subjects (mean age 4.8 years) were enrolled in an initial study of unblinded peanut oral immunotherapy at Duke and the University of Arkansas Medical Sciences Center. Comorbid allergic disease was prevalent in this cohort, with 68% having asthma, 64% atopic dermatitis, and 61% allergic rhinitis. 20 of 28 have completed the three phase protocol; four subjects dropped out of the study for personal reasons, one due to the development of eosinophilic esophagitis, and three remain in the build-up or maintenance phase.

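### All three related classes require a known response pattern, so a well-timed adverse event of a new kind has no class and, read literally, does not trigger the expedited reporting rules

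*Protocol*

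**What the plan says.** Protocol, Relationship to Procedure Definitions, opens the *associated* group with a broad standard: "There is a reasonable possibility that the adverse event may have been caused by the test product and/or procedure". The next sentence ties that standard to events placed in one of three classes, each with its own conditions:

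- *Definitely related*: a temporal sequence; the event "follows a known response pattern to the test article and/or procedure; and, when appropriate to the protocol", is confirmed by stopping and re-exposure; and no other reasonable explanation.
- *Probably related*: a reasonable temporal sequence; the event "follows a known response pattern to the test product and/or procedure, is confirmed by improvement after rechallenge"; and no other reasonable explanation.
- *Possibly related*: a reasonable temporal sequence, and the event "follows a known response pattern to the test product and/or procedure, but could have been produced by" the clinical state or other therapies.

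*Unrelated* needs both the absence of a reasonable temporal sequence and a more likely cause elsewhere. A negative rechallenge is named as supporting evidence. The *not associated* group above it asks for enough information to show that the cause lies elsewhere.

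Under Unexpected Adverse Event, an event is unexpected when "its nature (specificity) or severity is not consistent with applicable product information". Procedures and Monitoring gives two expedited rules. The first reads: "All unexpected serious adverse events related to the experimental procedures will be reported to the IRB, DCRU, DSMB, and FDA". The second sends other related events of Grade 3 and above to the IRB and DCRU. Adverse Events Collection Procedures leaves the relatedness decision to the Principal Investigator.

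**The concern.** The first expedited rule exists for harms that the product information does not foresee, and an event new in nature is the plainest example. The related classes pull the other way: each asks that the event already be recognised as something the product does. A rule that needs both unexpected and related then has no clear way to fire for a new kind of harm.

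Children enter at 9 to 36 months of age, take daily study product through build-up and 36 months of maintenance, and may be followed for up to 72 months. Toxicity Grading says that grading is meant to support assessment of treatment-related toxicity, and that assessment depends on these classes. An investigator who follows the class definitions and one who follows the opening sentence could reach different answers for the same child.

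The rechallenge wording adds a smaller problem. As printed, *probably related* asks for an observation that would count against relatedness.

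**Working it through.** The plan states no figure to reproduce, so the check is one of logic. Each class is built from four yes/no conditions taken from Relationship to Procedure Definitions: T, a reasonable temporal sequence; K, a known response pattern; D, improvement or rechallenge confirmation; E, another reasonable explanation. A new kind of event has K = no, which leaves 2 × 2 × 2 = 8 combinations of T, D and E.

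With T = no there are four combinations. The two with E = yes are *unrelated*; the two with E = no fit no class. With T = yes, which is the case that matters, there are four:

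| D | E | As written | Pattern condition dropped from *probably* and *possibly* | Same, with *possibly* as the floor |
|---|---|---|---|---|
| yes | no | no class | probably | probably |
| yes | yes | no class | possibly | possibly |
| no | yes | no class | possibly | possibly |
| no | no | no class | no class | possibly |
| Related | | 0 of 4 | 3 of 4 | 4 of 4 |

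As written, the eight combinations give 0 related, 2 unrelated and 2 + 4 = 6 without a class. *Unrelated* cannot absorb the four well-timed ones, because it requires that timing be implausible. The last row shows why removing the pattern condition from the two lower classes is not enough. An event with no improvement and no other explanation fails *probably* (no improvement), *possibly* (no alternative cause) and *definitely* (no known pattern).

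Next, the reporting rules:

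- The first expedited rule needs unexpected, serious and related. The third condition fails.
- The second needs related and Grade 3 or above. The first condition fails.

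Other routes do not use relatedness:

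- Study Stopping Rules halt the trial for a serious event, or an unanticipated event of Grade 3 or above, with the IRB and FDA consulted. The DSMB and DCRU are not named.
- Deaths are reportable within 24 hours.
- Serious events are recorded on case report forms and notified to the sponsor/investigator.
- Recording and Reporting Procedures provides semi-annual DSMB monitoring, with no relatedness filter stated.
- Expedited reports sent to other organisations, and the annual adverse event report to the IRB, are copied to the DCRU.

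What these leave uncovered is mainly prompt notice to the DSMB and the relatedness class itself.

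Last, rechallenge. *Definitely related* describes a positive rechallenge as the reaction coming back on repeat exposure. Improvement on rechallenge is the opposite result, and *unrelated* cites a negative rechallenge in its favour. Yet *probably related* asks that the event "is confirmed by improvement after rechallenge". *Definitely related* also attaches a first positive-rechallenge label to improvement after the product is stopped. In both places improvement after stopping is evidently meant.

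**The case against.** The best defence is that the text is ambiguous rather than closed. The phrase known response pattern is not defined and is not equated with product information. The *associated* group starts from reasonable possibility, and *not associated* needs positive information. Individual Stopping Rules uses another broad test, whether the investigator feels a serious event is potentially a result of participation. A sensible investigator could report a new harm under any of these. That stands as a limit on the likely effect. It does not settle which standard governs, because the opening sentence is applied through the three classes and nothing exempts new kinds of event from the pattern condition.

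Three stronger readings are tempting, and the documents do not support them:

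- A reader might infer that an unexpected event can never be classed as related. An event unexpected only in severity can follow a known pattern. So can one whose pattern is known from elsewhere but is absent from the protocol or consent.
- A reader might infer that one rechallenge result places an event in two opposite classes. It does not: *unrelated* also requires implausible timing and another likely cause, which *probably related* excludes.
- A reader might use the pilot withdrawal under Preliminary Results, "one due to the development of eosinophilic esophagitis", to count missed reports. The protocol already reports that case, the list of potential reactions under Adverse Event is open-ended, and nothing shows that the case was serious, as the first expedited rule requires.

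The backstops also stand. New serious harms would not go unseen, and since the SAP specifies no safety analysis, no effect on particular safety tables can be claimed.

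**Conclusion.** The point holds in a limited form. For a well-timed event of a new kind, the class definitions conflict with the reasonable-possibility standard that introduces them, and the two expedited rules inherit the conflict. The size is structural: 0 of 4 combinations can be classed as written. The documents give no basis for a number of affected children. The practical loss is chiefly the expedited DSMB report and a consistent relatedness classification.

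This rests on two assumptions: that related in Procedures and Monitoring carries its defined meaning, and that the definitions are applied as written. If investigators already work from reasonable possibility, the effect is small, but the text should say so. The two rechallenge phrases are wording errors whichever standard governs. The correction should be made: the gap is real and partly backstopped, and closing it costs little.

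**What to change.** Amend the protocol in four places:

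1. In Procedures and Monitoring, state that an event is related for both expedited rules when there is a reasonable possibility that the product or procedure caused it.
2. In *probably related* and *possibly related*, remove the known response pattern as a necessary condition. *Definitely related* may keep it.
3. Make *possibly related* the floor: any event with a reasonable temporal sequence that does not meet a higher class belongs there, whether or not another cause is possible and whether or not it improves when the product is stopped. This closes the fourth row of the table.
4. Correct the rechallenge wording under *probably related*, and the first positive-rechallenge label under *definitely related*, to improvement after stopping the product.

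The cost is a short text amendment. A few more events will be classed as related and reported. The two combinations with neither plausible timing nor another explanation remain without a class; they are outside this point but could be assigned in the same amendment.

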Subjects who miss one to two days of the daily dose will continue at their current dose at home. The PI will determine where the next dose of study protein is given for those who miss three to four days of the daily dose based on the length of time on study, the daily dose amount, the subject's reaction history and the amount of time since the last reaction to a dose in order to assure safety with dosing. Those who miss more than four days will return to the clinical research unit for evaluation by the study team in order to determine the best course of action for the subject. Options open to the investigator include repeat desensitization, observed dosing at a dosing level previously tolerated by the subject, or a change from active subject to control subject. To monitor subjects for adherence, any accidental ingestion, any symptoms related to daily dosing and any unintended side-effects of daily dosing, the families will be asked to keep a simple daily diary to record the requested information. A copy of the daily diary is included on page 16 of the protocol.

We will monitor accidental reactions to peanuts in each subject during the PMIT trial. We will note any reaction that occurs in a subject after the ingestion of peanuts, and record the type of symptoms (i.e., skin, respiratory, gastrointestinal, or cardiovascular). Pilot data from our previous studies indicate that home dosing is safe, with infrequent reactions which are typically mild. These data have identified several risk factors for reactions, which include dosing on an empty stomach, fever/illness, and activity/exercise shortly after dosing. Families of subjects will be asked to administer the study protein with additional food such as at snack or meal times, and during illness to hold the study protein and contact study personnel for instruction.

Because of the extreme risk to subjects, those experiencing severe symptoms during dosing or challenges such as respiratory failure, hypotension or other symptoms requiring ICU care will be withdrawn from the study. Additionally any subjects who have had an accidental peanut ingestion and developed anaphylaxis with respiratory failure or hypotension during the time on PMIT will be dropped from the active portion of the study. Subjects that do not complete the study because of an accidental reaction to peanut will be followed in the control group.

Study Stopping Rules

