12	100mg	2	25%
13	125mg	2	25%
14	156mg	2	25%
15	195mg	2	25%
16	245mg	2	25%
17	306mg	2	25%
18	383mg	2	25%
19	479mg	2	25%
20	599mg	2	25%
21	749mg	2	25%
22	936mg	2	25%
23	1170mg	2	25%
24	1463mg	2	25%
25	1829mg	2	25%
26	2286mg	2	25%
27	3000mg	2	31%

Tolerance of Daily Study Protein Dose Diary

Child's Name _____

Date							
Dose taken (Yes or No)							
Accidental ingestion (Yes or No)							

Using the following scale, please enter the appropriate number in each box
 0 = None 1 = Mild 2 = Moderate 3 = Excessive

Vomiting							
Diarrhea							
Hives							
Itching							
Runny Nose							
Wheezing							
Other							

Comments:

DEVIL Screening Form

Screening _____ Date _____
Recorded by _____

Informed consent obtained and witnessed prior to obtaining information: Yes No

Copy of informed consent given to parent: Yes No

Name _____ Unit # _____

Parent's Name _____

Address _____

Telephone number that we can personally reach you: (H) _____
(W) _____ (Cell) _____

DOB _____ Age _____ (between 9 and 36 months of age)

Sex: Male Female Race: Afr-American Caucasian Hispanic Other

Weight _____ (lb kg) Height _____ (in cm)

Ever eaten peanut? Yes No Not Sure

Describe reactions to peanut and other foods:

Eligibility Criteria

_____ Subject between 9 and 36 years of age

_____ Peanut allergy diagnosis within the last 6 months: CAP > 0.35 or PST > 3mm with history of peanut ingestion & convincing IgE-mediated symptoms within 60 minutes

date of reaction: _____

date of testing (and results): PST _____ (_____) CAP _____ (_____)

Or

_____ Probable peanut allergy diagnosis within the last 6 months: CAP > 5 and PST > 3mm with NO history of peanut ingestion

date of testing (and results): PST _____ (_____) CAP _____ (_____)

Exclusion

_____ Subjects with a history of severe, anaphylaxis to peanut

_____ Medical history that would prevent a DBPCFC/OFC to peanut

Desensitization Day

Initial Medical History & Physical Exam

Subject Name: _____ D.O.B: _____

Subject # _____ Race: _____

Atopic History: (Symptoms, triggers, current treatment, date of onset/diagnosis)

Rhinitis _____

Atopic Dermatitis _____

Food Allergy _____

Drug/Venom allergy _____

Asthma _____

Patient has a current in-date EpiPen

Yes: Date expires _____

No:

Patient was given an EpiPen

Yes: Date expires _____

No:

Episodic symptoms/brief and intermittent with complete clearing/ greater than twice a week/continuous?

_____ Coughing _____ Chest Tightness _____ Wheezing _____ SOB

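### The home diary has no row for several expected reactions (abdominal pain, cough or hoarseness, swelling) and no treatment field, so these events risk under-recording and are not captured in structured form

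*Protocol*

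**What the plan says.** The Protocol section on study design, dosage schedule and accidental reactions gives the diary its purpose. To monitor adherence, accidental ingestion, and also "any symptoms related to daily dosing and any unintended side-effects of daily dosing, the families will be asked to keep a simple daily diary".

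The form itself (Tolerance of Daily Study Protein Dose Diary) has yes/no lines for dose taken and accidental ingestion. It then says "Using the following scale, please enter the appropriate number in each box", with the scale "0 = None 1 = Mild 2 = Moderate 3 = Excessive". The rows are Vomiting, Diarrhea, Hives, Itching, Runny Nose, Wheezing and Other. A free-text Comments space follows.

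Three other parts of the Protocol bear on it:

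- **Expected reactions** (Definitions, Adverse Event). These include "gastrointestinal manifestations such as vomiting, diarrhea, or abdominal pain", and also angioedema, coughing and hoarseness.
- **Individual Stopping Rules.** Subjects leave daily dosing for "moderate to severe clinical symptoms (GI, respiratory or skin) at home after taking the daily dose of peanut protein". Participation also stops for "recurrent abdominal pain, or recurrent emesis which is felt by the PI to be potentially dose related".
- **Procedures and Monitoring.** "Reactions to dosing of the study product will be recorded on a dosing log and will not be reported separately as adverse events". Only a reaction that meets the criteria for a serious adverse event goes on an adverse event form as well.

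**The concern.** Nearly all doses in this trial are taken at home, and the diary is the form the family fills in at the time. A symptom with its own row is asked about every day. A symptom without one is recorded only if the parent thinks to score Other and then explains the score in Comments. Several reactions that the protocol itself expects fall in the second group, and so does any medication given.

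At stake is the completeness of home safety information. It informs the investigator's stopping decisions and the early-challenge condition of no severe symptoms in the preceding six months. It is also the natural source for any description of home reactions by body system or by treatment, which is how the pilot data are presented in Preliminary Results, Tables 1 and 2.

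**Working it through.** The plan gives no figure for this point, so the check sets the forms side by side.

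**Step 1. Expected reactions against the forms.**

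| Expected reaction | Home diary | Clinic Symptom Scoring Sheet |
|---|---|---|
| Vomiting, diarrhea | Own rows | IV.B, objective complaints |
| Abdominal pain | No row; Other only | IV.A, subjective complaints |
| Pruritus | Itching | I.C |
| Urticaria | Hives | I.D, joined with angioedema |
| Angioedema | No row; Other only | I.D |
| Nasal symptoms | Runny Nose | II.B and II.C |
| Cough | No row; Other only | II.D, laryngeal |
| Hoarseness (throat) | No row; Other only | II.D |
| Wheezing | Own row | III.A |
| Treatment given | No field; Comments only | Challenge Sheet: antihistamine and epinephrine, yes/no with route |

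Of abdominal pain, cough, throat symptoms and swelling, 0 of 4 have their own row and 4 of 4 can be entered under Other. If two occur on one day they share a single 0-3 score.

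**Step 2. What the diary can yield.** It can give a rate of any symptom per dosing day, and a rate for each of the six listed symptoms. Rates for the unlisted symptoms, or for treated doses, depend on unprompted comments. On a day with both a study dose and an accidental ingestion, the grid does not show which one a symptom followed.

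**Step 3. What the other records add.**

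- The dosing log holds dosing reactions, but its layout is not shown. For home doses its content must come from the family.
- The Follow-Up Visit form takes an interval history, accidental ingestion or reaction, an abdominal examination, the last antihistamine with its indication, and current medications. A last antihistamine is one entry, not a count.
- Families are told to call staff with concerns. These calls are started by the family.
- Adverse event reporting is a backstop only for serious reactions.

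**Step 4. Scale, as an indication only.** Build-up from 6 mg to 3000 mg in Table 3 takes 20 two-week intervals: 20 × 14 = 280 days. Full maintenance is 36 × 30.4 = 1,094 days, so a child completing it takes about 280 + 1,094 = 1,374 home doses. A child finishing at 12 months of maintenance takes about 280 + 365 = 645.

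- Abdominal symptoms followed 0.9% of pilot home doses (95% CI 0.6% to 1.4%). Then 1,374 × 0.009 = 12 per child (8 to 19 over the interval), or 645 × 0.009 = 6 with early completion.
- Treatment of any kind followed 67 of 10,184 pilot home doses. Then 1,374 × 67/10,184 = 9 per child, or 645 × 67/10,184 = 4.

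The abdominal count includes vomiting and diarrhea, which do have rows. The share that is pain alone is not given, so 12 is a ceiling on pain-only doses at the pilot rate. None of these figures counts events lost.

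**The case against.** The strongest reply is that nothing is truly unrecordable. Other and Comments sit on the same page, the dosing log is a second record, build-up visits come every ten to fourteen days with a history form, and families can call. The protocol also chose a simple diary for a task that lasts years, and each extra row costs some compliance. All of this stands. It limits the point to under-recording and lack of structure.

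Three stronger readings are tempting, and the documents do not support them.

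- **That home-reaction rates or recurrent abdominal pain cannot be measured.** Any-symptom and listed-symptom rates can be derived, the rest can be written in, and the unseen dosing log may hold more.
- **That the abdominal-pain stopping rule depends on how diligently families comment.** The rule is an investigator's judgement with no diary threshold, and no text makes the diary its only source.
- **That the SAP's low-dose safety advantage rests on under-recorded reactions.** The SAP's Sample size section mentions a better safety profile only conditionally, as one of several possible advantages, and plans no home-reaction analysis. Both dose arms use the same diary and families are blinded to dose, so no bias between arms is identified.

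The pilot rates are also weak support for scale. That study was unblinded with a mean age of 4.8 years, whereas this trial enrols at 9 to 36 months.

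What survives is the mismatch between the forms: the protocol asks clinic staff about these symptoms separately and does not ask families about them at all.

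**Conclusion.** The point holds as a minor matter of form design and is a cheap improvement. The diary leaves out several reactions that the protocol expects, and treatment given. With non-serious dosing reactions kept out of adverse event reporting, these home events risk under-recording, and the diary does not give their rates in structured form. They inform the investigator-judged stopping rules and the six-month look-back before early challenge.

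No under-recording is demonstrated, no planned estimate is shown to fail, and the comparison of dose arms is not shown to be affected. The conclusion assumes that prompted items are reported more completely than unprompted ones, and that the dosing log does not already collect the same items from families. If it does, the gap reduces to saying so in the protocol.

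**What to change.** Revise the one-page diary:

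- Add rows for abdominal pain, cough or throat symptoms, and swelling, matched to the categories on the clinic scoring sheet so that home and supervised doses can be tabulated alike. That sheet joins swelling with urticaria, so the two diary rows can be combined for comparison.
- Add a tick box for medication given.
- Add a mark for whether symptoms followed the study dose or accidental peanut.

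State in the protocol which record, diary or dosing log, feeds the investigator's stopping review and the safety tables. The clinical stopping rules themselves are not touched.

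The cost is a form revision and a slightly longer daily entry for families. For that reason nothing beyond these items, such as time since the dose, is asked for.
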